2.5.3 Handling of intercurrent events

As described in [Section 1.2.1](#), the intercurrent events will be handled according to a hypothetical strategy, reflecting a scenario in which a given participant with an event had not actually experienced the event. To enable this strategy, depending on the type of event, either (1) the biomarker assessment at the visit immediately following the event will be set to missing for the primary analysis or (2) all subsequent biomarker assessments will be set to missing for the primary analysis, as described in that section. The exception to this is changes to standard of care cardiovascular disease prevention medication, which will be handled by a treatment policy strategy, in which any occurrence of the event is ignored and the subsequent data are included in the analysis.

The data from these assessments will be estimated in the primary analysis under the assumption that the outcome in the affected participant would be no different than in the population of participants assigned to the same treatment but that did not experience the event.

Although measurements collected after the events handled by this strategy are not used for the analysis, the planned assessments will take place for possible evaluation of supportive estimands.

A listing of all intercurrent events will be provided.

2.5.4 Handling of missing values not related to intercurrent event

If no measurements are collected after the intercurrent event is experienced, these missing measurements will not be imputed. Missing data not related to intercurrent events are expected to be intermittent and will be assumed to be missing at random. These data will not be explicitly imputed.

2.5.5 Sensitivity analyses

As a sensitivity analysis to the Emax model described in [Section 2.5.2](#), a Hill coefficient other than 1 may be explored.

If the Emax model converges on either of the two primary endpoints, the traditional model previously described will be performed as a sensitivity analysis on that endpoint and/or to assess MAS825 effect.

2.5.6 Supplementary analyses

As a supplementary analysis, the primary analysis may be performed as described, except that some or all biomarker measurements collected after any change in standard of care cardiovascular disease prevention medication may be excluded from the analysis.

Further supplementary analyses will be performed: 1) excluding participants with BLQ value for the baseline primary outcome, and 2) by CHIP-mutation subtype.

Finally a supplementary analysis including all data available, without any exclusion due to Intercurrent Events (IEs), will also be provided.

2.6 Analysis supporting secondary objectives

The secondary objective is to evaluate the safety, tolerability, and pharmacokinetics of DFV890/MAS825 in participants with coronary heart disease and CHIP.

2.6.1 Secondary endpoint(s)

The secondary endpoints include safety endpoints (adverse events, vital signs, electrocardiograms, and laboratory assessments) and PK endpoints: plasma trough concentrations (C_{trough}) of DFV890 at steady state, and MAS825 serum concentrations.

2.6.2 Statistical hypothesis, model, and method of analysis

Analysis of safety endpoints refers to [Section 2.7](#).

PK set will be used for PK analysis. Summary statistics of C_{trough} of DFV890 and plasma concentrations collected at day 92 will be provided by dose and time point including the frequency of concentrations below the LLOQ and reported as zero. Time will be defined at the

dosing period level. MAS825 serum concentrations will be summarized in the same way. Note that while DFV890 will be assessed over a 3-week period (4-week considering the EOS assessment), MAS825 PK will be assessed over a 12 week period.

Summary statistics will include mean (arithmetic and geometric), standard deviation (SD), and CV (arithmetic and geometric), median, minimum, and maximum concentration.

2.6.3 Handling of intercurrent events

Not applicable.

2.6.4 Handling of missing values not related to intercurrent event

Drug concentrations below LLOQ will be treated as missing for the calculation of the geometric means and geometric coefficient of variation (CV%), and as zero for all other calculations.

2.6.5 Sensitivity analyses

Not applicable.

2.6.6 Supplementary analyses

Not applicable.

2.7 Safety analyses

The safety set will be used for all safety analyses

2.7.1 Adverse events (AEs)

Treatment-emergent AEs (TEAEs) are those with an onset after the start of a specific dosing period, or which were present prior to the start of the dosing period but increased in severity, changed from being not suspected to being suspected of study treatment relationship, or developed into SAEs after the start of the dosing period.

AEs with an onset outside the on-treatment period (before first dosing or more than 30 days from last dosing) will be just listed. AEs with a day of onset coinciding with the start of a new treatment will be assigned to the new treatment. Therefore AEs occurred on Day 1 will be considered TEAEs.

AE summaries will include all TEAEs occurred in the on-treatment period. All AEs collected in the AE CRF page will be listed by treatment sequence and participant, along with the information collected on those AEs e.g. AE relationship to study drug, AE outcome, etc.

AE summaries will be provided by treatment and by treatment sequence.

Summaries by treatment will be restricted to TEAEs occurred in the dosing periods (excluding TEAEs occurred in the follow-up) and percentages will be derived on the total number of dosing periods involved. This means that a participant treated with placebo for four 3-week treatment periods (as in treatment sequence 5) will be counted 4 times. Similarly, the same AE occurred in x separate dosing periods will be counted x times.

MAS825 dosing sessions will be defined as a 12-week interval from day 1 to Day 85 study visits.

Summaries by treatment sequence will consider all TEAEs occurred in the on-treatment period and will be referred to the number of participants assigned to each sequence.

An overview summary table will be provided reporting dosing sessions/participants with TEAEs (overall and by severity), treatment-related TEAEs (overall and by severity), serious TEAEs, and TEAEs/drug-related TEAEs leading to discontinuation of study treatment .

The number (and percentage) of dosing sessions/participants with TEAEs will be summarized by primary system organ class, and preferred term. An additional summary by primary system organ class, preferred term, and maximum severity will also be reported, as well as for serious (including fatal) TEAEs.

A participant with multiple AEs within a preferred term/primary system organ class is only counted once towards the total of the preferred term/primary system organ class. In the analyses based on dosing sessions this rule will be applied at each dosing session level.

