1.3 Schedule of activities (SoA)

The SoA lists all of the assessments when they are performed. All data obtained from these assessments must be supported in the participant’s source documentation. The “X” in the table denotes the assessments to be recorded in the clinical database or received electronically from a vendor. The “S” in the table denotes the assessments that are only in the participant’s source documentation and do not need to be recorded in the clinical database.

Participants should be seen for all visits/assessments as outlined in the SoA or as close to the designated day/time as possible. Missed or rescheduled visits should not lead to automatic discontinuation.

Participants who discontinue from study should be scheduled for a final evaluation visit if they agree, as soon as possible, at which time all of the assessments listed for the EOS visit will be performed. At this final visit, all dispensed investigational product should be reconciled, and the adverse events (AEs) and concomitant medications not previously reported must be recorded on the Case Report Form (CRF).

Every effort will be made to take pharmacokinetic (PK) samples at the protocol-specified time.

The preferred sequence of assessments and data collection during study visits is shown below in [Figure 1-2](#). For visits during which the participant is scheduled to take study treatment, all assessments will be conducted pre-dose administration.

Figure 1-2 Recommended order of assessments

As per [Section 4.5](#), during a public health emergency as declared by local or regional authorities, i.e., pandemic, epidemic or natural disaster that limits or prevents on-site study visits, alternative methods of providing continuing care may be implemented by the Investigator as the situation dictates. If allowable by a local health authority, national and local regulations and depending on operational capabilities, phone calls, virtual contacts (e.g., tele consultation) or visits by site staff/ off-site healthcare professional(s) (OHP) staff to the participant's home, can replace certain protocol assessments, for the duration of the disruption until it is safe for the participant to visit the site again. If the Investigator delegates tasks to an OHP, the Investigator must ensure the individual(s) is/are qualified and appropriately trained to perform assigned duties. The Investigator must oversee their conduct and remain responsible for the evaluation of the data collected.

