2.1.1.3 Dosing period

A dosing period is defined as an approximate 3-week interval between scheduled visits as given in the study design figure ([Figure 1-1](#)). For example, dosing period 1 will begin at Day 1 (randomization) and it is expected to end on the Day 22 visit, at which point the next treatment will be administered according to the specific treatment sequence. All assessments will be done before the dosing of the next dosing period. Specifically:

Dosing period 1: Begins at Day 1 (randomization) and ends on max (Day 22 visit, last dose in dosing period 1) prior to next dosing level.

Dosing period 2: Begins immediately after the end of dosing period 1 and ends on max (Day 43 visit, last dose in dosing period 2) prior to the next dosing level.

Dosing period 3: Begins immediately after the end of dosing period 2 and ends on max (Day 64 visit, last dose in dosing period 3) prior to the next dosing level.

Dosing period 4: Begins immediately after the end of dosing period 3 and ends on max (Day 85 visit, last dosing in period 4).

The Follow-up period begins immediately after the last dosing period.

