In the analyses by treatment and timepoint, the time will be referred to the start of each dosing period. Therefore for instance a day 43 assessment will be considered a 3-week assessment and assigned to the treatment received by the participant in the second dosing period (except in treatment sequence 1). Time will be managed differently for the participants randomized to treatment sequences 1 and 5. In this case time will be referred to the start of the first treatment (MAS825 in treatment sequence 1, Placebo for treatment sequence 5). Therefore for these participants assessments after 6, 9 and 12 weeks will also be derived.

Analyses by treatment won't be performed for the laboratory data collected just at the start and at the end of the trial (Coagulation panel and Urinalysis).

In the analyses by treatment sequence and timepoints the following time points will be reported:: screening, baseline, Days 22, 43, 64, 85 and 92.

Box-plots by treatment sequence and time, as well as by treatment will be provided. In the latter case the horizontal axis will include the baseline and the 3-week assessments. Weeks 6,9,12 distributions will be plotted just for the placebo and the MAS arm. Further details will be included in the TFL shells document.

Listing for participants with lab values outside the normal range (per normal ranges provided in the source dataset) will be provided. If there is any abnormal lab value for a participant, all measurements of this lab value for the participant will be presented in this listing with the abnormal values flagged.

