2.7.4.2 Vital signs

All vital signs data (absolute values and changes from baseline) will be summarized by treatment/treatment sequence and time. Time will be managed as previously described for labs data. All vital signs data will be listed by treatment sequence and time. Box-plots by treatment sequence and time as well as by treatment will be provided.

A listing for complete vital signs data for all participants will be presented with the abnormalities flagged according to the following rules:

Notable criteria (High/Low):

- Systolic blood pressure [mmHg]: >140/<90 mmHg
- Diastolic blood pressure [mmHg]: >90/<50 mmHg
- Pulse rate [bpm]: >90/<40 bpm
- Weight [kg]: >110/<35 Kg
- Temperature [°C]: >37.5/<35.0°C.

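### SAP 2.7.1's same-day rule credits AEs that are dated to Day 22, 43 or 64 and arise from that visit's pre-dose assessments to a dose not yet taken

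*SAP*

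**What the plan says.** **AE rule.** SAP 2.7.1 decides ties by calendar day: "AEs with a day of onset coinciding with the start of a new treatment will be assigned to the new treatment". It makes no exception for findings made before that day's dose. By-treatment AE percentages use dosing periods as the denominator; by-sequence percentages use participants.

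**Order of events at the visit.** Protocol 1.3 says: "For visits during which the participant is scheduled to take study treatment, all assessments will be conducted pre-dose administration". Footnote 2 of Table 1-2 repeats this for Days 1, 22, 43 and 64. SAP 2.1.1.3 agrees: "All assessments will be done before the dosing of the next dosing period". It also closes each dosing period at the visit, ahead of the next dose level. Under protocol 6.2.3, participants wait for site staff before taking the dose on a visit day.

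**Laboratory and vital-sign values from the same visit.** SAP 2.7.3 gives the example that "a day 43 assessment will be considered a 3-week assessment and assigned to the treatment received by the participant in the second dosing period", which is the period that is ending. For vital signs SAP 2.7.4.2 says: "Time will be managed as previously described for labs data".

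**What can become an AE at these visits.** Protocol 8.6.1 lets AEs be detected through examination and laboratory findings, and 8.4.4 requires abnormal laboratory results to be assessed as possible AEs. Chemistry, hematology, vital signs and a brief examination with rash assessment take place on each of Days 22, 43 and 64.

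**The concern.** A finding made before a dose cannot have been caused by it. If a neutrophil decrease is measured in the Day 43 pre-dose sample and recorded as an AE starting on Day 43, SAP 2.7.1 counts it under the third period's dose. The value itself enters the by-treatment laboratory summaries and box-plots under the second period's dose.

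The by-treatment tables are where AEs are compared between DFV890 doses and placebo. Decreases in neutrophils and white cells, and skin rash, are named DFV890 risks (protocol 2.3.1.3 and 2.3.2.1), and protocol 4.3 describes the exposure relationship for skin reactions as poorly understood. Dose attribution is therefore something these tables will be read for. The sequences only go up, so misassignments cannot cancel by moving in both directions.

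**Working it through.** **Inputs.** SAP 2.1.1.2 gives the sequences: 2 = placebo, 10, 25, 100 mg; 3 = placebo, 25, 50, 100 mg; 4 = 10, 25, 50, 100 mg; 5 = placebo throughout. SAP section 3 gives the planned numbers: 8, 8, 2 and 2. No dropout is assumed. Sequence 1 is excluded because SAP 2.7.1 treats it as one 12-week MAS825 session.

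**Check against the plan's own figure.** SAP 2.4.1 expects twenty-four placebo sessions. The count is 8 (Sequence 2) + 8 (Sequence 3) + 2 × 4 (Sequence 5) = 24, which agrees. The other sessions are 10 mg: 8 + 2 = 10; 25 mg: 8 + 8 + 2 = 18; 50 mg: 8 + 2 = 10; 100 mg: 8 + 8 + 2 = 18.

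**Visit days at issue.** 20 participants × 3 visits (Days 22, 43, 64) = 60.

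- Placebo to 10 mg: 8
- Placebo to 25 mg: 8
- 10 to 25 mg: 8 + 2 = 10
- 25 to 50 mg: 8 + 2 = 10
- 25 to 100 mg: 8
- 50 to 100 mg: 8 + 2 = 10
- Placebo to placebo: 2 × 3 = 6

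The first six rows sum to 54 visits before a higher dose. Of these, 8 + 8 = 16 go from placebo to an active dose and 8 + 10 = 18 go into 100 mg.

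**Where a pre-dose finding dated to the visit day is counted.**

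| Treatment | Sessions | Visit days if credited to the ending period | Visit days under SAP 2.7.1 |
|---|---|---|---|
| Placebo | 24 | 22 | 6 |
| 10 mg | 10 | 10 | 8 |
| 25 mg | 18 | 18 | 18 |
| 50 mg | 10 | 10 | 10 |
| 100 mg | 18 | 0 | 18 |

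The totals for 25 mg and 50 mg do not change, although the visits behind them do. Day 85 is left out because it starts no new treatment; it adds 18 days to 100 mg and 2 to placebo under either rule.

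**Effect of one event.** If a session's only event is moved, the rate changes by 1/24 = 4.2 points for placebo, 1/10 = 10.0 points for 10 or 50 mg, and 1/18 = 5.6 points for 25 or 100 mg.

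**Possible number of events.** The documents give no rate. Assume that each of the 54 visits yields such an AE with the same probability p, including within the placebo-to-active and into-100-mg subsets.

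| p | Moved upward (54p) | Placebo to active (16p) | Into 100 mg (18p) |
|---|---|---|---|
| 0 | 0 | 0 | 0 |
| 1% | 0.5 | 0.2 | 0.2 |
| 5% | 2.7 | 0.8 | 0.9 |
| 10% | 5.4 | 1.6 | 1.8 |

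These are AE counts. The tables count a session once per preferred term or organ class, so table cells change by no more than this and possibly less.

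**The case against.** **The rule is a reasonable convention.** The protocol requires start and end dates for AEs, not clock times, and 6.2.3 lists Days 22, 43 and 64 as first days of the new periods. For an event that begins after the new dose, or at an unknown time that day, assignment to the new treatment is sound. This stands, and the point does not reach those events.

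**Few AEs may qualify.** The rule depends on onset date, not on when the event was found. A rash or symptom elicited at the visit but dated earlier stays with the earlier period. Table 4-1 expects most AEs, rash especially, within the first 17 days of dosing, which argues against rash onsets clustering on Day 22. That stands for rash but does not settle laboratory findings. No passage says whether a laboratory AE is dated to the sample or to the result.

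**The bias is cautious.** Pushing events to a higher dose is conservative when active drug is compared with placebo. It does not help in judging at which dose a finding starts: an event arising on 25 mg may be shown under 100 mg. The by-treatment tables are descriptive, and participant listings let each event be traced.

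**Two stronger readings are not supported.** A reader might infer that SAP 2.7.1 contradicts itself on Day 1, since it says both "AEs with an onset outside the on-treatment period (before first dosing or more than 30 days from last dosing) will be just listed" and "Therefore AEs occurred on Day 1 will be considered TEAEs". SAP 2.1.1.10 starts the on-treatment period at Day 1, and the second sentence is the specific rule, so Day 1 is settled by stated convention. A reader might also infer that the laboratory tables will report the same abnormality under another dose. By treatment, SAP 2.7.3 plans values, changes from baseline and box-plots; low/high shift tables are by sequence only. The mismatch is between an AE count and a summarised value, not between two counts of abnormalities.

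**Conclusion.** The point holds in a narrow form, and it is minor. SAP 2.7.1 is wrong only for AEs dated to a Day 22, 43 or 64 visit that are findings from that visit's pre-dose assessments. For those, the by-treatment AE tables name a dose that had not been taken, at odds with the SAP's own period definition and its handling of laboratory and vital-sign values. Earlier-dated AEs, same-day AEs that begin after the dose, by-sequence tables and listings are not affected.

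The direction is certain: all 54 visits at which the treatment changes lead to a higher dose. The size is not known. The counts assume planned numbers and no dropout, and they measure opportunity. The effect is probably small, though with 10 to 24 sessions per treatment a single event is visible in a percentage.

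**What to change.** Add to SAP 2.7.1 that an AE with onset on a Day 22, 43 or 64 visit day is assigned to the dosing period just ended in either of two cases:

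- it corresponds to a laboratory or vital-sign value from that visit's pre-dose assessment that is new or worsened relative to the previous visit;
- it corresponds to an examination finding that the site confirms was present before that day's dose.

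All other same-day AEs stay with the new treatment. Requiring a new or worsened value keeps a true post-dose event in a participant with a long-standing abnormality from being moved back.

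Laboratory and vital-sign values are already in the database. Physical examinations carry code S, meaning that they sit only in "source documentation and do not need to be recorded in the clinical database", so they need a site query. Unclear cases should be settled before database lock by people without treatment codes, such as the blinded investigator. Protocol 6.3.2 gives the statistician, programmers and other analysis staff access to the codes, so they should not decide.

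Add one sensitivity by-treatment AE table with all Day 22, 43 and 64 same-day AEs assigned to the prior period. Label it a bound, because it also moves genuine post-dose events back.

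The cost is one SAP paragraph, one programming rule, a few queries, a short review before lock and one table; no new assessments are needed. Two limits remain: the examination match relies on a retrospective answer, and a laboratory AE dated to a later result date is not caught.

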9.3.2 Statistical model, hypothesis, and method of analysis

The primary analysis for DFV890 will assess the effect on the change in IL-6 and IL-18 compared to placebo in a dose-response model, separately for the two biomarkers.

An E_{\max} model will be fit to the post-baseline values for each biomarker, with a random effect (reflecting between-participant variability) on the placebo response E_0 and on ED_{50} (the dose that produces half the maximal effect), a covariate on E_0 for the baseline value of the biomarker, and a covariate on ED_{50} for baseline body weight. All biomarker measurements will be logarithm-transformed prior to the analysis.

An additional random effect reflecting between-participant variability on E_{\max} may be incorporated if the data allows.

Additional details of the model will be specified in the Statistical Analysis Plan (SAP).

From the model, the predicted response at each treatment and associated 80% CI will be extracted, along with the difference to placebo for each DFV890 dose level, the corresponding 2-sided 80% CI. The estimated response and the difference to placebo will be back-transformed and reported on the ratio scale.

In case of convergence issues, a linear mixed effects model will be fit in place of the E_{\max} model (to be referred to as 'traditional model'). The model will include treatment as a fixed effect, a random intercept effect for participant, and the baseline value of the biomarker and baseline body weight as covariates. All biomarker measurements will be logarithm-transformed prior to the analysis.

The least square (LS) mean and associated 80% CI for each treatment, and the estimated mean difference to placebo for each DFV890 dose level and 2-sided 80% CI will be extracted from the model and back-transformed to the ratio scale for reporting.

The primary analysis for MAS825 will assess the effect on the change in IL-6 compared to placebo after 3 weeks of treatment. For this analysis, the Week 3 measurements of IL-6 on MAS825 and all Week 3 (i.e., Dosing Period 1) placebo measurements from the other sequences will be used.

A linear model of IL-6 at Week 3 with treatment as a fixed effect, and the baseline value of the biomarker as a covariate will be used for the analysis. All biomarker measurements will be logarithm-transformed prior to the analysis.

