9.4.1 Safety endpoints

For all safety analyses, the safety set will be used. All listings and tables will be presented by treatment sequence.

Adverse events

The number (and percentage) of participants with treatment emergent AEs will be summarized by overall count, by treatment/dose, primary system organ class, and preferred term. An additional summary by treatment sequence primary system organ class, preferred term, and maximum severity will be reported.

Treatment-emergent AEs are those with an onset after the start of a specific dosing period, or which were present prior to the start of the dosing period but increased in severity, changed from being not suspected to being suspected of study treatment relationship, or developed into SAEs after the start of the dosing period.

For the purposes of these summaries, a dosing period is defined as an approximate 3-week interval between scheduled visits as given in the study design figure ([Figure 1-1](#)). For example, the first dosing period will begin at Day 1 (randomization) and end on the Day 22 visit, at which point the next treatment will be administered according to the specific treatment sequence.

A participant with multiple AEs within a primary system organ class is only counted once towards the total of the primary system organ class.

All information obtained on AEs will be displayed by treatment sequence and participant.

A participant with multiple AEs within a primary system organ class is only counted once towards the total of the primary system organ class.

AEs which will be counted for a specific treatment period are those which are treatment-emergent. These events are those with an onset after the start of the treatment period, or which were present prior to the start of the treatment period but increased in severity, changed from being not suspected to being suspected of study treatment relationship, or developed into SAEs after the start of the treatment period.

Vital signs

All vital signs data will be summarized by overall count (%) and by treatment/dose and visit/time.

12-lead ECG

All ECG data will be summarized by overall count (%) and by treatment/dose and visit/time.

Clinical laboratory evaluations

All laboratory data will be summarized by overall count (%) and by treatment/dose, and visit/time. An additional summary by treatment sequence, will be reported.

Immunogenicity

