2.4 Treatments (study treatment, rescue medication, concomitant therapies, compliance)

2.4.1 Study treatment / compliance

Study treatment compliance will be descriptively summarized by study treatment for the safety analysis set, including compliance in different percent categories, (< 20%, between 20% and < 40%, between 40% and <60%, between 60% and < 80%, >= 80%) as derived considering protocol deviation codes. This analysis will be performed in terms of dosing sessions considering a potential sample size of twenty-four 3-week dosing sessions with placebo. Note that treatments with MAS825 and DFV placebo won't be included in this analysis being assigned to MAS825 treatment.

Study treatment duration (in days), defined as last date of administration – first date of administration +1, will also be summarized by treatment.

Compliance data will also be listed by treatment sequence.

This analysis will be restricted to DFV890/DFV890 placebo sessions excluding the participants randomized to the first treatment sequence.

Details regarding MAS825, MAS825 placebo, DVF890 placebo administrations in participants treated previously with MAS825, will be only listed by treatment sequence and treatment.

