The assumed true E_{max} is approximately -0.5, or $\log(0.6)$, representing a 40% reduction.

From the model-based quantities, the following efficacy criteria will be evaluated at the median baseline value of the biomarker and the median baseline body weight:

1. At least one of the following is observed in relation to placebo at the 100 mg dose:
 - IL-6 reduction \geq 25%, or

- IL-6 reduction $\geq 20\%$ + IL-18 reduction $\geq 10\%$, or
 - IL-6 reduction $\geq 15\%$ + IL-18 reduction $\geq 20\%$.
2. For any of the above criteria that are achieved, the one-sided p-value for the comparison of DFV890 vs. placebo for the associated biomarker(s) is less than 0.1.

Simulations have shown that there is at least 80% power in achieving statistical significance at the 10% level and the mean effect as shown above (with type 1 error of $\leq 10\%$)

This allocation of participants will also provide at least 80% power of showing a statistically significant difference between MAS825 and pooled placebo, if the true effect of MAS825 on IL-6 is a 45% reduction (i.e., $\log(0.55)=0.60$, there is no effect on placebo, and the between subject SD of IL-6 is ≤ 0.5 using a 1 sided alpha of 10%.)

If MAS825 is not different from placebo, there will be a 10% chance of achieving the efficacy criteria (Type 1 error).

4 Change to protocol specified analyses

This SAP is based on the analyses described in the study protocol. Additional details and clarifications have been introduced to provide a more accurate description of the statistical plan.

5 Appendix

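### By-treatment adverse event percentages set a 12-week MAS825 risk beside 3-week placebo and DFV890 risks, with no exposure adjustment

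*SAP*

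**What the plan says.** SAP 2.7.1 plans AE summaries by treatment and by treatment sequence. In the by-treatment version, "percentages will be derived on the total number of dosing periods involved", so a Sequence 5 participant enters the placebo column four times. A participant with several events under one preferred term or system organ class counts once for it, and "In the analyses based on dosing sessions this rule will be applied at each dosing session level". For the antibody, "MAS825 dosing sessions will be defined as a 12-week interval from day 1 to Day 85 study visits".

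Protocol 9.4.1 sets the unit differently: "For the purposes of these summaries, a dosing period is defined as an approximate 3-week interval between scheduled visits". It makes no exception for MAS825. SAP section 4, which is meant to list changes from the protocol, says only that "Additional details and clarifications have been introduced to provide a more accurate description of the statistical plan".

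For laboratory data, SAP 2.7.3 does deal with timing: "Time will be managed differently for the participants randomized to treatment sequences 1 and 5", with both sequences timed from their first treatment. SAP 2.7.4.2 handles vital signs in the same way. The by-treatment AE tables have no such rule.

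**The concern.** A percentage of sessions with an event depends on how long each session lasts. When one column covers 12 weeks and the others about 3, the long column reads higher even if the drugs behave identically. A reader scanning the by-treatment table would see an apparent MAS825 excess over placebo that comes only from the longer window.

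Safety and tolerability of MAS825 is a secondary objective, and Protocol 4.2 justifies placebo partly as the comparator for an unbiased safety assessment. Nothing else in the planned output would show the exposure gap in numbers: the treatment-duration summary in SAP 2.4.1 is restricted to DFV890 and DFV890-placebo sessions and leaves out Sequence 1.

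Assigning Sequence 1 events after week 3 to MAS825 is not in dispute. SAP 2.1.1.2 gives the reason, namely that the effect is expected to persist. The problem is only the unequal window.

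**Working it through.** **Inputs.** SAP section 3 gives 28 participants in ratio 4:4:4:1:1, that is 8, 8, 8, 2 and 2. SAP 2.1.1.2 gives the treatment in each period of each sequence. The 3-week AE risk p is in neither document, so it is an assumption and is varied.

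**Denominators.**
- Placebo: 8 (Sequence 2) + 8 (Sequence 3) + 2 × 4 (Sequence 5) = 24. This reproduces the SAP's own figure in 2.4.1, "considering a potential sample size of twenty-four 3-week dosing sessions with placebo".
- DFV890: 10 mg 8 + 2 = 10; 25 mg 8 + 8 + 2 = 18; 50 mg 8 + 2 = 10; 100 mg 8 + 8 + 2 = 18.
- MAS825: 8 sessions of 12 weeks.

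**Ratio when nothing differs but the window.** With the same constant rate on both treatments, the 12-week risk is 1-(1-p)^4 and the ratio to the 3-week risk is [1-(1-p)^4]/p.

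| 3-week risk p | 12-week risk | Ratio |
|---|---|---|
| 1% | 3.9% | 3.94 |
| 5% | 18.5% | 3.71 |
| 10% | 34.4% | 3.44 |
| 20% | 59.0% | 2.95 |
| 40% | 87.0% | 2.18 |
| 50% | 93.8% | 1.88 |

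The limits of 1 and 4 do not need independence between periods. With equal marginal risk p per period, the chance of at least one event in four periods lies between p and 4p.

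**Between-participant heterogeneity.** Take gamma frailty with variance v and the same 3-week risk: H = ((1-p)^(-v) - 1)/v, and the 12-week risk is 1-(1+4vH)^(-1/v). For v = 0.5 and 1 the ratio is 3.24 and 3.08 at p = 10%, and 2.69 and 2.50 at p = 20%.

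**What the table would show with no drug effect.** At p = 10% the expected counts are 8 × 0.344 = 2.75 of 8 on MAS825 and 24 × 0.10 = 2.4 of 24 on placebo. The probabilities below are exact, comparing Bin(8, 1-(1-p)^4) with Bin(24, p). At least double also requires at least one MAS825 event.

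| p | MAS825 % above placebo % | MAS825 % at least double |
|---|---|---|
| 1% | 0.28 | 0.27 |
| 5% | 0.77 | 0.68 |
| 10% | 0.90 | 0.78 |

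In a common 3-week window at p = 10%, Bin(8, 0.10) against Bin(18, 0.10), the two probabilities fall to 0.46 and 0.32. Sessions are treated as independent here, although Sequence 5 gives four per participant.

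**Does time at risk remove the bias?** The weekly hazard at p = 10% is -ln(0.9)/3 = 0.0351. Expected weeks at risk, stopping at the first event, are 2.4/0.0351 = 68.3 for placebo and 2.75/0.0351 = 78.3 for MAS825. Both rates are 3.51 per 100 weeks, so the ratio is 1.

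**Does planned exposure work instead?** No. Planned exposure is 24 × 3 = 72 weeks on placebo and 8 × 12 = 96 on MAS825. At p = 10%, (2.75/96)/(2.4/72) = 0.86. At p = 20%, (4.72/96)/(4.8/72) = 0.74. Dividing first events by planned exposure over-corrects.

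**The case against.** **The figure is right for what it is.** The MAS825 percentage is a valid 12-week risk, the SAP states the window openly, and no test or go/no-go rule uses it. All of this stands. It limits the consequence to a misleading comparison between columns and does not remove that comparison.

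**An equal-window table is already planned.** The by-sequence summaries count participants over the whole on-treatment period, so planned duration is the same for every sequence. But the only placebo-only group there is Sequence 5, with about 2 participants; Sequences 2 and 3 move to active drug after Dosing Period 1. The other 16 placebo sessions appear as placebo only in the by-treatment table. The laboratory approach also rests on Sequence 5 alone for placebo beyond week 3, so it shows that the SAP recognised the timing problem and is no stronger as a comparison.

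**The protocol change may be a clarification.** The protocol's dosing period is tied to up-titration, and Sequence 1 has a single active dose. That is arguable, but Protocol 9.4.1 defines the unit for these summaries without an exception, so a line in SAP section 4 is warranted.

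**The size depends on assumptions.** This is correct. At p = 1% the ratio is near its maximum, yet MAS825 exceeds placebo with probability only 0.28, because events are few. Events clustered soon after the injection would lower the ratio.

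**Footnotes may sit in the table shells.** The separate TFL document is not available, so labelling cannot be judged. The absence of an exposure-adjusted rate from the protocol and SAP can be.

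**Conclusion.** The concern holds. Followed as written, SAP 2.7.1 puts a 12-week risk in 8 MAS825 sessions beside 3-week risks in 24 placebo sessions and in 10 to 18 sessions per DFV890 dose. At equal AE rates the MAS825 percentage is larger by a factor between 1 and 4: close to 4 for rare terms and well below that for common ones, such as an any-event row.

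The range assumes equal risk in each period and nominal session lengths. Protocol 6.2.3 allows a dosing period of 17 to 35 days, which would move the upper limit to between 84/35 = 2.4 and 84/17 = 4.9. The tabulated ratios also assume a constant hazard.

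The distortion affects a descriptive secondary-objective output and has no bearing on the primary analysis. It should be corrected because the correction is simple and the by-sequence table cannot stand in for it.

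**What to change.** In SAP 2.7.1, add one or both of the following to the by-treatment AE tables:

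1. Exposure-adjusted first-event incidence: sessions with an event divided by participant-weeks at risk, with time stopped at the first event.
2. A common-window comparison of MAS825 from Day 1 to Day 22 (8 participants) with Dosing Period 1 placebo (8 + 8 + 2 = 18 participants). Protocol 9.3.2 already uses this comparator for the MAS825 IL-6 analysis: "all Week 3 (i.e., Dosing Period 1) placebo measurements from the other sequences will be used".

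Also state the session length for each column in a footnote, keep the 12-week by-sequence view, and record the change from Protocol 9.4.1 in SAP section 4.

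Two apparent remedies should be avoided. Planned exposure as the denominator over-corrects, as shown above. Splitting MAS825 into 8 × 4 = 32 three-week sessions dilutes early reactions: an event in 1 of 8 participants (12.5%) would read as 1 of 32 (3.1%).

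The cost is SAP wording and some extra table programming, with no new data. The incidence rate assumes a roughly constant hazard, and the common window ignores MAS825 events after week 3, so the 12-week view must stay beside them. With 8 MAS825 participants, either comparison will be imprecise.
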